3.1 Masking

To prevent bias, several steps will be taken to keep the investigators and subjects masked to the identity of the assigned solution:

- Subjects will be identified by subject numbers, which are unrelated to study solution assignments.
- Solution bottles will be over-labelled ('A', 'B' or 'C') and packaged in kit-boxes so that the identity of the study solution is not revealed. Therefore, investigators must only dispense solutions for the study that have been provided by the sponsor or clinical research organisation (CRO).
- If for any reason the investigator needs to be unmasked to the solution type that the study subject is using, they should follow the decoding procedures which will be present in the investigator study binder.

If required, for purposes of a subject's safe clinical management, the investigators will be able to learn the identity of the solution being used by contacting the study Clinical Research Associate (CRA).

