7.5 Visit 1b: Lens Fitting and Dispensing

The subjects will undergo a trial fit with the randomly allocated study lens type. If the appropriate study lenses are not available, a dispensing visit will be scheduled for another day.

- i. Slit lamp – confirm continued eligibility if on a different day
- ii. Record the parameters of the lenses on the Dispensing eCRF (lens type / lot number, lens parameters, etc.).

The performance of the lenses should be assessed after 10-15 minutes settling time and the following variables will be assessed:

- iii. Subjective comfort (0-10)

- iv. Vision
 - Monocular HC DVA (with CL)
 - Spherical over-refraction (SOR)
 - Monocular HC DVA with SOR
 - Binocular distance VA with CLs (Snellen/logMAR to the nearest letter)
- v. Surface characteristics
 - Lens surface wetting (0-4) and reason if Grade 1 or less.
- vi. Lens fit
 - Centration (0-2)
 - Corneal coverage (Y/N)
 - Post-blink movement (0-4)
 - Tightness on push-up (0-4)
 - Overall fit acceptance (0-4) and reason if Grade 2 or less.

To be successfully dispensed, subjects must show >Grade 2 lens fit acceptance with the trial lens and must be correctable to 6/12 (20/40) (0.30 LogMAR) or better in each eye. Trial lenses must also show >Grade 1 wettability.

Modifications to optimize the lens power will be allowed.

If the lens fit is acceptable, the investigator will issue the care system (Kit-box containing solution, lens case and instructions) that the subject was randomized to, and complete the Kit-box Accountability Log. All kit-boxes must be accounted for, even if they are not dispensed.

- vii. The subject will be instructed to wear the lenses on a daily wear basis (at least 8 hours a day, 6 days per week) until the 1-week follow-up appointment, unless they experience a problem which warrants lens removal. In this case the subject should contact the investigator.
- viii. The investigator or a clinical assistant will review the Participant Information Guide with the subject, which describes the procedures for contact lens wear, lens care, handling, cleaning and disinfecting. Any subject, who does not follow instructions to a degree that, in the Sponsor or Investigator's opinion, jeopardizes the subject's wellbeing or the validity of the study, will be discontinued.
- ix. The investigator will complete the Source Document Record (Appendix 3).

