7.6 Subject Discontinuation

Subjects will be discontinued from the study in the event of any of the following occurring:

- i. Unacceptable subjective discomfort (i.e. lens cannot be tolerated or worn)
- ii. Unacceptable slit lamp findings (i.e. clinically significant, Grade 3 or 4)
- iii. Unacceptable fit (i.e. lens too tight or too loose)
- iv. At the discretion of the investigator or the subject

In the event of discontinuation, the Study Exit eCRF must be completed and the study exit date recorded on the source document record. The investigator will indicate the primary reason for discontinuation by selecting one of the boxes provided on the Exit eCRF. Further details can be provided in the 'comments' section if necessary.

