10.2 Statistical Analysis Plan

General considerations: All data summaries and statistical analyses will be performed using the SAS software Version 9.4 or higher (SAS Institute, Cary, NC). Throughout the analysis of data, the results for each subject/eye will be used when available for summarization and statistical analysis. Missing data will be excluded from the analysis. Unscheduled visits will be excluded from the statistical analysis.

Descriptive statistics will be reported by solution type at baseline, dispensing, and each follow-up visit according to ISO 11980:2012. Continuous variables will be summarized using sample size (N), mean, standard deviation (SD), minimum and maximum, and categorical data variables will be summarized using the sample size, frequency distribution (count and percentage of subjects or eyes in each category), mean, median and SD.

Analysis Population: Statistical Analysis for hypothesis testing will be performed on all evaluable subjects. All inference will be carried out with an overall type I error rate controlled at 0.05.

Analysis of comfort: Results will be analyzed using a linear mixed model including the experimental design factors: solution type, visit and their interaction will be included as fixed effect factors and site and subject as random effects.

Comparisons between the test and control solutions will be carried out using pairwise one-sided confidence intervals constructed for least-square mean differences (mean difference calculated as Test minus Control). Non-inferiority will be concluded if the lower confidence limit is greater than -1.0.

Analysis of visual acuity: Results will be analyzed using a linear mixed model including the experimental design factors: solution type, visit and their interaction will be included as fixed effect factors and site and subject as random effects.

Comparisons between the test and control solutions will be carried out using pairwise one-sided confidence intervals constructed for least-square mean differences (mean difference calculated as Test minus Control). Non-inferiority will be concluded if the upper confidence limit is less than +0.05 logMAR.

Analysis of wettability: Results will be analyzed using a linear mixed model including the experimental design factors: solution type, visit and their interaction will be included as fixed effect factors and site and subject as random effects.

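### All seven non-inferiority tests use an undefined evaluable set, with no as-randomised or as-dispensed analysis to show whether exclusions affect the result

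*Combined protocol and SAP*

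**What the plan says.** Section 2.1 sets seven non-inferiority hypotheses: comfort, visual acuity, wettability, deposits, corneal staining, limbal hyperemia and bulbar hyperemia. Section 10.2 gives them one analysis population: "Statistical Analysis for hypothesis testing will be performed on all evaluable subjects". The word *evaluable* appears nowhere else in the document and has no definition. No second population is planned for inference.

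The same section settles which data count. It says "Missing data will be excluded from the analysis" and "Unscheduled visits will be excluded from the statistical analysis". It also says that "the results for each subject/eye will be used when available for summarization and statistical analysis".

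Three other places bear on who leaves and who decides:

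- Section 7.6 discontinues subjects for discomfort that prevents wear and for Grade 3 or 4 slit lamp findings, among other grounds. Section 4.7 rules out replacement.
- Section 7.5, item viii, covers a subject whose failure to follow instructions, in the opinion of the sponsor or the investigator, puts at risk the subject's "wellbeing or the validity of the study, will be discontinued".
- Section 3.1 says that "several steps will be taken to keep the investigators and subjects masked to the identity of the assigned solution". Section 5.1 likewise names subjects and investigators. Neither mentions the sponsor, the CRO or the biostatistician.

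**The concern.** Evaluability cannot be known at assignment, so this set is presumably fixed after randomisation, although the plan does not say when or by whom. Two documented routes could thin it in a way related to outcome.

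The first needs no one's discretion. Comfort, corneal staining and hyperemia are tested endpoints, and poor results on them are grounds for discontinuation. A subject who leaves before the 1-week visit, or whose bad finding is recorded at an unscheduled visit, supplies no such value to the test.

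The second is the opinion-based discontinuation for non-compliance. A subject who dislikes a solution may also use it irregularly, so the two can overlap.

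If either route removes more poor results from the test arm than from the control arm, the comparison moves towards non-inferiority. With a single, undefined inferential set, no planned test would show whether the conclusion depends on who was left out.

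**Working it through.** **Inputs**

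- 200 enrolled, 133 test and 67 control (synopsis, section 4.2). At least 180 completers (synopsis). Drop-out below 10% (section 10.1).
- Bounds: 1.0 for comfort, 0.05 logMAR for visual acuity, 0.5 grade for the other five (section 2.1).
- One-sided intervals with overall type I error 0.05 (section 10.2). The confidence level of each interval is not stated, so one-sided 0.05 and 0.025 are both shown.
- No SD, power or expected difference is stated. The error rates in step 2 are in SD units and do not depend on the SD.

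**Step 1: the plan's own figure.** 180 / (1 − 0.10) = 200. Split 2:1, 200 × 2/3 = 133.3 and 200 / 3 = 66.7. The plan's 200, 133 and 67 are reproduced. Losses at the 10% limit are 200 − 180 = 20. In proportion that is about 13 test (13/133 = 9.8%) and 7 control (7/67 = 10.4%).

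**Step 2: false non-inferiority when the worst subjects are lost.** Assumptions: normal outcome, one value per subject, true difference exactly at the margin, 133 v 67, pooled one-sided t limit, 20,000 simulated trials per setting. The poorest k subjects are removed from the stated arm.

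| Lost: test / control | Shift in difference (SD) | Error at 0.05 | Error at 0.025 |
|---|---|---|---|
| 0 / 0 | 0.00 | 5.1% | 2.6% |
| 3 / 0 | 0.055 | 11% | 6% |
| 7 / 0 | 0.111 | 21% | 13% |
| 13 / 0 | 0.188 | 40% | 29% |
| 20 / 0 | 0.275 | 63% | 51% |
| 13 / 7 | −0.011 | 6.6% | 3.8% |

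A check on scale: the standard error with everyone included is √(1/133 + 1/67) = √(0.00752 + 0.01493) = 0.150 SD. Losing the 13 worst test subjects therefore moves the estimate by 0.188 / 0.150, about 1.25 standard errors. The last row shows that the inflation comes from unequal loss, not from loss as such.

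**Step 3: how much can be hidden.** If a fraction w of the test arm is lost and those subjects average g worse than the ones kept, the test mean shifts by w × g.

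- 13 lost, 2 grades worse: (13/133) × 2 = 0.20, against a bound of 0.5.
- 13 lost, 5 comfort points worse: (13/133) × 5 = 0.49, against a bound of 1.0.
- Shifting by a whole bound with 13 lost needs g = 0.5 / 0.0977 = 5.1 grades or 1.0 / 0.0977 = 10.2 comfort points. Both are off the scale.
- With all 20 losses in the test arm (20/133 = 0.150), it needs 3.3 grades or 6.65 comfort points. That is on the scale but extreme.

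Selective loss within the planned drop-out could turn a borderline failure into a pass. It could not conceal an arbitrarily large difference.

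**The case against.** An evaluable or per-protocol set is common in non-inferiority trials. Keeping non-compliers can dilute a real difference and so favour non-inferiority, which means an as-dispensed set is not automatically the cautious choice. This stands. It is a reason to want both sets, and not a defence of one undefined set.

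Discontinuation is not deletion. Nothing says that a discontinued subject's data are removed. A mixed model with visit as a factor can use 1-week results from a subject who leaves later, and *evaluable* might simply mean anyone with usable data. This also stands in part, but it depends on the missing definition. It does not help a subject with no scheduled follow-up visit.

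The restriction covers hypothesis tests only. Descriptive statistics by solution, the occurrence of Grade 2 or higher findings and ocular adverse events are also planned, and section 7.6 has a primary reason recorded for each discontinuation. A reader would therefore see something of the losses, but these summaries carry no bound and no test.

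A reader might infer that an unmasked sponsor can drop poor performers from the test arm. The documents do not support that. The study is described as double-masked, and the text is silent on whether sponsor or CRO staff who might decide on exclusions know the code. Section 3.1 lets an investigator learn a subject's solution through the CRA for safe clinical management. This implies that the CRO can reach the key, but not that those deciding exclusions hold it. The sponsor's power under section 7.5 is limited to serious non-compliance, applies equally to both arms, and is not linked anywhere to evaluability.

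**Conclusion.** The point holds as a gap in the analysis plan. All seven tests depend on one undefined set. Outcome-driven discontinuation, opinion-based discontinuation and the exclusion of missing data and unscheduled visits can all affect what enters that set, and no planned inferential analysis would reveal the effect.

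The size is conditional. At one-sided 0.05 and a true difference at the margin, the error rises from about 5% to between 11% and 40% if the 3 to 13 worst test subjects alone are lost. It stays at about 6.6% if the worst subjects leave both arms in proportion. These are assumption-based worst cases and not predictions: they rest on normal outcomes, one value per subject and removal of exactly the poorest results. It does not follow that the evaluable set must favour the test solution. The bias needs losses that differ by arm, and the documents give no evidence either way. The change should be made because it is cheap and the plan otherwise has no check.

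**What to change.** In section 10.2:

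1. Add a non-inferiority analysis, with the same models and bounds, of all subjects dispensed a study solution, analysed by assigned solution and using all available scheduled-visit data whatever the compliance. Starting from dispensing is sound because trial-fit failures occur before the kit-box is issued, so they cannot reflect experience of the solution.
2. Define *evaluable* by listed, objective criteria and keep it as the companion set.
3. Claim non-inferiority only if both sets meet the bound.
4. Add a sensitivity analysis that includes exit and unscheduled-visit data from subjects discontinued early. Item 1 alone does not recover these results. Section 7.7 already requires presenting VA and slit lamp variables at every unscheduled visit, so for those endpoints no new data collection is needed.
5. Have existing staff without the A/B/C key fix membership of the evaluable set in writing before the key is released, and report exclusions by arm and reason.

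The cost is SAP wording, one or two extra model runs, and a claim that must hold in two sets. Sample size and visits do not change.

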2 STUDY OBJECTIVES

To test whether the Oté Sensation multi-purpose solution is substantially equivalent to another multi-purpose solution (Bausch & Lomb BioTrue).

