2.1 Primary Hypotheses

2.1.1 Efficacy Hypotheses

The Oté Sensation multi-purpose solution will be non-inferior to the Bausch & Lomb BioTrue solution in terms of:

Comfort (0-10), a non-inferior bound of 1.0 will be used.

Visual acuity (logMAR VA), a non-inferiority bound of 0.05 will be used

Wettability (0-4), a non-inferior bound of 0.5 will be used.

Deposits (*in situ* 0-4), a non-inferior bound of 0.5 will be used.

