7.4 Visit 1a: Baseline

The subjects should attend the first visit wearing their habitual lenses.

If they are not wearing their lenses, reschedule the visit.

The following procedures will be conducted on all subjects:

- i. Allow the subject to read the Participant Information Sheet and Informed Consent and explain the nature, purpose, risks of the study etc. If he/she is agreeable, ask the subject to sign the Informed Consent Form and initial where appropriate. The investigator (or person taking the consent) should also sign the consent form. Provide the subject with a copy and retain the original.
- ii. The subject is assigned with a Subject ID number according to the Enrolment Log. Subjects must be enrolled sequentially. Enter details on Enrolment Log as outlined on the form.

Baseline Measurements and Eligibility:

The following baseline measurements will be recorded on the Baseline eCRF:

- i. Subject demographics (age, sex, medications and associated medical history, allergies)
- ii. Habitual lens comfort (on insertion, during the day and prior to removal, 0-10)
- iii. Symptoms, problems and complaints
- iv. Vision
 - Subjective vision quality: distance (0-10 scale)
 - Monocular high contrast (HC) visual acuity (VA) with CLs (Snellen/logMAR to the nearest letter)
 - Spherical over-refraction (SOR)
 - Monocular and binocular HC DVA with SOR
- v. Wearing times – habitual lenses:
 - Wearing time at visit
 - Typical insertion time
 - Typical removal time
 - Typical time CL comfort deteriorates
 - Maximum wearing time in last month (hrs.)
 - Days worn per week
- vi. Details of habitual lenses and care system:
 - Lens brand
 - Care system brand

- vii. Rewetting drop usage (type and frequency),
- viii. Lens surface characteristics - habitual lenses
 - Lens surface wetting (0-4)
 - Lens deposits (film: 0-4; no. of white spots)
- ix. Lens fit - habitual lenses
 - Centration (0-2)
 - Corneal coverage (Y/N)
 - Post-blink movement (0-4)
 - Tightness on push-up (0-4)
 - Overall fit acceptance (0-4) and reason if Grade 2 or less.
- x. Remove habitual lenses
- xi. Full ocular health
- xii. Monocular spherocylindrical refraction and monocular HC distance VAs (logMAR or Snellen to the nearest letter)
- xiii. Biometry: Horizontal visible iris diameter (HVID), palpebral aperture (PA), keratometry (D/mm)
- xiv. Slit lamp examination
 - Limbal hyperemia (0-4)
 - Bulbar hyperemia (0-4)
 - Stromal edema (0-4)
 - Vascularization (0-4)

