Comparisons between the test and control solutions will be carried out using pairwise one-sided confidence intervals constructed for least-square mean differences (mean difference calculated as Test minus Control). Non-inferiority will be concluded if the lower confidence limit is greater than -0.5.

Analysis of deposits: Results will be analyzed using a linear mixed model including the experimental design factors: solution type, visit and their interaction will be included as fixed effect factors and site and subject as random effects.

Comparisons between the test and control solutions will be carried out using pairwise one-sided confidence intervals constructed for least-square mean differences (mean difference calculated as Test minus Control). Non-inferiority will be concluded if the upper confidence limit is less than +0.5.

Analysis of slit lamp findings: First the results will be averaged across each sector. Average results will be analyzed using a linear mixed model including the experimental design factors: solution type, visit and their interaction will be included as fixed effect factors and site and subject as random effects.

Comparisons between the test and control solutions will be carried out using pairwise one-sided confidence intervals constructed for least-square mean differences (mean difference calculated as Test minus Control). Non-inferiority will be concluded if the upper confidence limit is less than +0.5.

Additional analyses:

- Overall occurrence of slit lamp findings of Grade 2 or higher
- Overall occurrence of lens VA findings worse than 6/12 (20/40)
- Overall occurrence of clinically significant lens surface deposits (>Grade 1)
- Ocular adverse events.

Any deviations from the above analysis will be documented in the report.

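### Section 10.2 states an overall type I error of 0.05 but omits the success rule, interval level, visit contrast and comfort rating needed to secure it

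*Combined protocol and SAP*

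**What the plan says.** Section 2 gives one objective: "To test whether the Oté Sensation multi-purpose solution is substantially equivalent to another multi-purpose solution (Bausch & Lomb BioTrue"). Under Primary Hypotheses, section 2.1.1 lists four efficacy endpoints (comfort, visual acuity, wettability, deposits) and section 2.1.2 three safety endpoints (corneal staining, limbal hyperemia, bulbar hyperemia). Both lists open with "The Oté Sensation multi-purpose solution will be non-inferior to the Bausch & Lomb BioTrue solution in terms of", and each endpoint has its own bound.

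Section 10.2 promises that "All inference will be carried out with an overall type I error rate controlled at 0.05". It then has five rule paragraphs; the slit lamp paragraph serves all three safety endpoints. Each uses "pairwise one-sided confidence intervals constructed for least-square mean differences" and ends with its own conclusion, for example "Non-inferiority will be concluded if the lower confidence limit is greater than -1.0" for comfort and "Non-inferiority will be concluded if the upper confidence limit is less than +0.5" for slit lamp findings. No paragraph refers to another.

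Each model has solution, visit and their interaction as fixed effects, with site and subject as random effects. The visits entering the model are not listed. Follow-up is at 1 week and 1 month (section 7.2.1). On the unit of analysis, "the results for each subject/eye will be used when available for summarization and statistical analysis".

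At each follow-up, comfort is rated on insertion, during the day and before removal, and VA with lenses is measured in three ways: monocular, monocular with over-refraction, and binocular (sections 7.5.2 and 7.5.3). Section 2.1.1 specifies only comfort on a 0–10 scale and logMAR VA.

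**The concern.** An overall error rate is a property of a set of tests and a rule for combining them. The plan names the rate but leaves open:

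1. whether all seven endpoints must pass or each is a claim of its own;
2. the multiplicity method, if they are separate claims;
3. the confidence level of the one-sided limits (95% and 97.5% both fit the text);
4. which least-squares mean difference decides: 1 week, 1 month, both, either, or an average;
5. which comfort rating is tested and, less seriously, which VA measure.

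A reader of the report could not verify the 0.05 or know what result supports substantial equivalence. The deciding visit or comfort rating could also be settled after the data are seen without departing from the written plan, so the requirement in section 10.2 to document deviations would not catch it.

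A related gap affects the limits themselves. If both eyes contribute records and the contrast is at one visit, a model with only site and subject random effects does not represent the correlation between two eyes at the same visit, or within one eye across visits.

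**Working it through.** **Inputs from the documents.** Overall alpha 0.05; seven endpoints; two follow-up visits; three comfort ratings; no interim analysis (section 10.3). No correlations, SDs or power are given, so correlations and variance shares below are assumptions, shown as ranges.

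**The plan's own figure.** If equivalence is claimed only when all seven pass, the error cannot exceed that of the single test whose endpoint is at its bound. With one fixed contrast and measure at one-sided 0.05, that is at most 0.05. The stated figure is reproduced, but only under this rule.

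**Other readings.** For k exchangeable normal test statistics with correlation ρ and z = z(1−α):

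P(at least one rejects) = 1 − ∫ φ(g) Φ[(z − √ρ·g)/√(1−ρ)]^k dg,

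which is 1 − (1−α)^k at ρ = 0; for k = 7, 1 − 0.95^7 = 0.302. For two visits, P(both reject) = 2α − P(at least one rejects); at ρ = 0.5, 0.100 − 0.0878 = 0.0122.

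| Reading | One-sided 0.05 | One-sided 0.025 |
|---|---|---|
| All seven, fixed contrast and measure | at most 5% | at most 2.5% |
| All seven at both visits, one endpoint at its bound | 1.2–2.5% | 0.5–1.1% |
| All seven, either visit may decide, one endpoint at its bound | 7.5–8.8% | 3.9–4.5% |
| Separate claims, one endpoint at its bound | 5% | 2.5% |
| Separate claims, two at bound | 8.8–9.8% | 4.5–4.9% |
| Separate claims, three at bound | 11.8–14.3% | 6.3–7.3% |
| Separate claims, all seven at bound | 20.3–30.2% | 11.5–16.2% |

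Visit correlation is 0.5 to 0.8, with the other six endpoints clearly inside their bounds. Endpoint correlation is 0.5 (lower figure) to 0 (higher figure), on one fixed contrast. If any of the three comfort ratings could decide, the comfort test alone has the k = 3 error: 11.8–14.3% at 0.05 and 6.3–7.3% at 0.025.

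**Adjusted separate claims.** 0.05/7 = 0.00714 gives 1 − (1 − 0.00714)^7 = 4.9% at correlation 0 and 3.8% at 0.5, with visit and measure fixed. If either visit may also support a claim, the same limit gives 6.0–9.0% (visit correlation 0.8 to 0.5, endpoint correlation 0.5 to 0). 0.05/14 = 0.00357 restores control, since 14 × 0.00357 = 0.05.

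**Standard error for eye-level outcomes.** Take two eyes and two follow-up visits in the model, omit site, and let the variances be s (subject), sv (subject-by-visit), se (eye-within-subject) and e (residual). For one subject's two-eye mean at one visit:

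- true variance = s + sv + se/2 + e/2
- model variance, with subject and residual only = s + 2sv/3 + 2se/3 + e/2
- true minus model = sv/3 − se/6, which is zero only if sv = se/2

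| (s, sv, se, e) | Model SE / true SE | Actual error at nominal 5% |
|---|---|---|
| 0.2, 0.7, 0, 0.1 | 0.869 | 7.7% |
| 0.4, 0.4, 0, 0.2 | 0.923 | 6.4% |
| 0.4, 0.3, 0.1, 0.2 | 0.950 | 5.9% |
| 0.5, 0.2, 0.1, 0.2 | 0.970 | 5.5% |
| 0.4, 0.1, 0.2, 0.3 | 1.000 | 5.0% |
| 0.3, 0.1, 0.4, 0.2 | 1.024 | 4.6% |

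The follow-up average, and outcomes recorded once per subject, are not affected.

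**The case against.** The tempting stronger reading is that the trial runs at a 20–30% false-positive rate. The documents do not support that. The sentence in section 10.2 is itself a commitment to 0.05, which unadjusted separate claims would breach, and a single objective followed by lists of what the product must be non-inferior on leans towards requiring all seven. Under that rule, with contrast and measure fixed, 0.05 holds. The 20–30% also needs all seven endpoints exactly at their bounds. This stands, and limits the point to a missing method. It does not remove it: the lists are not a decision rule, and an all-seven requirement does not fix the visit or the level.

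A reader might also infer that letting either visit decide must break 0.05. That is true at one-sided 95% but not at 97.5%, where two visits give at most 2 × 0.025 = 0.05. As the level is unwritten, it belongs among the gaps.

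VA is less open than comfort. At follow-up and baseline the logMAR label is attached to monocular VA with the lens, and the additional analyses in section 10.2 speak of lens VA. The label moves to binocular VA only at dispensing (section 7.5), before the solution is used. Monocular VA with the lens is probably meant and needs only confirming.

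The covariance point rests on assumed variance shares, its direction is unknown, and four of the six cases lie within 4.6–5.9%. It is secondary, and applies only to eye-level records with a visit-specific contrast.

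**Conclusion.** The concern holds as a stated property that the written rules do not secure; it is not proven inflation. Applied literally as separate unadjusted claims, the five rule paragraphs do not deliver 0.05 at one-sided 95% once two or more endpoints are at their bounds. At one-sided 97.5% two endpoints stay below 5%, but the extreme case of all seven does not. With all seven required on a fixed contrast and measure, 0.05 is met. The sizes rest on exchangeable normal statistics with assumed correlations; that the answer depends on the unstated choices does not. The model's standard error is wrong for visit-specific eye-level contrasts except in one special case, by an amount the documents cannot settle. The plan should be amended before analysis.

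**What to change.** In section 10.2, state that substantial equivalence is concluded only if all seven bounds are met, each with a one-sided 95% limit, on one pre-named contrast: a named visit, or the average of the 1-week and 1-month visits only. Name one comfort rating and one VA measure, and label all other visits and measures supportive. This holds 0.05 without adjustment. The average should exclude baseline because "The subjects should attend the first visit wearing their habitual lenses", before the study solution is used; including it would dilute a true comfort difference of 1.0 at both follow-ups to (0 + 1.0 + 1.0)/3 = 0.67. The plan does not say that baseline enters the model.

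If separate endpoint claims are wanted, use one-sided 0.00714 each with visit and measure also fixed, or 0.00357 if either visit may support a claim.

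For eye-level outcomes with a visit-specific contrast, average the two eyes within each visit and use an unstructured covariance across visits, or add subject-by-visit and eye-within-subject random effects.

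The cost is wording and one covariance option, with no new data. The joint claim is harder to win: if each endpoint had 95% power, joint power would be 70–80% (0.95^7 = 0.698 at correlation 0, 0.797 at 0.5); at 99% each, 93–95%. These powers are assumed. With limits at 0.00714, each limit lies 2.450/1.645 = 1.49 times as far from its estimate (the non-inferiority bounds do not change), and 95% power per endpoint falls to 80%. With the covariance change, visit-specific intervals could widen by up to about 15% (1/0.869) or narrow by about 2% (1/1.024).
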